Study Title: Health Coaching & Technology in a Weight Loss Center

NCT#: NCT03309787

Date: 6 May 2019

Documents: Study protocol (includes statistical analysis plan)

SPECIFIC AIMS

The obesity epidemic affects 37% of adults¹ and leads to major morbidity², absenteeism³, mortality⁴ and high health costs⁵. Effective obesity therapy goals are to attain weight loss through healthy lifestyle changes⁶, reduce cardiac risk⁶, and prevent chronic illness. Integrating practical and sustainable approaches in obesity care can improve short- and long-term outcomes⁶. Nurse or physician-delivered Intensive Behavioral Therapy (IBT) using the 5 A's (ask, advise, assess, assist, arrange)^{7,8}, motivational interviewing^{9,10}, and goal setting¹¹ is the standard behavioral treatment for achieving a healthy weight and sustained lifestyle changes. In recent studies, trained health coaches have successfully used IBT to assist patients in improving health outcomes^{12,13}.

Despite the potential benefits of IBT¹⁰, access to trained providers is notably limited for rural adults^{14,15} who face high obesity rates and related morbidity¹⁶. Barriers to accessing evidence-based obesity care include the need to travel distances for clinic visits, absence of local specialized obesity-related services, and the lack of trained staff in remote areas^{17,18}. Telehealth offers practical and cost-effective solutions in overcoming such accessibility barriers¹⁹ to obesity treatment and health promotion approaches. Yet, even when patients achieve weight loss, maintaining their weight is difficult²⁰. Wearable monitors using adaptable sensors offer health care providers a means to obtain real-time information over time. Providing biometric measures and real-time data for motivation and feedback can augment standard obesity strategies and be delivered by health coaches^{12,13}.

Our goal is to identify effective, accessible, and sustainable means for improving long-term lasting weight loss, using scalable health-promoting devices in rural obese adults. This proposal aims to conduct a study of remote health monitoring using *Amulet*²¹, a Dartmouth Computer Science developed mobile health (mHealth) device, incorporated into usual health coach visits and delivered in patients' homes using video-conferencing. *Amulet* provides an adaptable platform for behavioral change; unlike commercial devices, it uses an open source programming model capable of testing an array of other strategies and non-proprietary devices²¹. We previously described the challenges in delivering obesity care^{22,23} and promises of virtual modalities in overcoming geographic barriers to care²⁴. However, use of technology in isolation, without human interactions, is unlikely to lead to success²⁵. Hence, we propose an eHealth-delivered health coaching obesity intervention that delivers IBT by trained health coaches using telehealth and *Amulet* to enhance behavioral change. Our rationale is to pilot the intervention with 30 Dartmouth-Hitchcock (D-H) Weight & Wellness Center patients to determine its potential effectiveness on weight loss, physical function, self-reported health, and care pathways in a specialty obesity clinic. If effective, the program will enhance in-home care and be disseminated to remote, low resource areas to rural obese adults lacking access to care. We will address the following Specific Aims:

Aim 1: Evaluate the feasibility and acceptability of an eHealth-delivered (remote monitoring and video-conferencing) health coaching obesity intervention in a rural, academic, specialty obesity clinic.

H1: An eHealth-delivered health coaching obesity intervention using video-conferencing and remote monitoring is: a) feasible (>80% of subjects will enroll; >80% of enrollees will complete the intervention); and b) acceptable in rural adults seeking treatment for obesity (using semi-structured interviews and Yip's Telemedicine survey).

Aim 2: Assess the potential effectiveness of an eHealth-delivered health coaching obesity intervention in improving weight, physical function and self-reported health in adults with obesity.

H2: Measures of improved weight (>5% loss), physical function (6-minute walk) & self-reported health (patient-reported outcome measurement system-PROMIS) will allow reliable estimates for designing an evaluative trial.

Aim 3: Ascertain the extent to which the intervention works within an existing specialty obesity clinic on implementation outcomes such as workflow adoption, organizational change and compatibility.

H3: Implementation will be adopted into the workflow (qualitative interviews and Haug's measure), lead to organizational change (General Organizational Index) and be perceived as having value (Willingness to Pay).

A transdisciplinary team will execute a pilot study for conducting a Type 2 hybrid effectiveness-implementation design²⁶ of this T3/T4 intervention. Expected outcomes include its feasibility and acceptability, the value added to specialized obesity care by improving outcomes, and the potential for eHealth integration into practice. The pilot builds logically to an R01 grant addressing critical gaps in pragmatic obesity strategies to improve health and care delivery pathways to with limited access to specialty care for long-term weight loss.

SIGNIFICANCE

Standard obesity advice within primary care is often ineffective in the long-term^{27,28}, which can amplify the morbidity observed in this population. The need to refer to specialty obesity care is needed⁶, yet access to care is lacking, especially in rural areas²⁴. Most evidence-based practices require busy clinicians to add visits²⁹ for direct, in-person IBT. These pathways are impractical due to workforce shortages, time constraints, and caseloads^{30,31}. Health coaches can assist in mitigating such challenges by effectively delivering IBT at higher

value¹³, allowing clinicians to focus on other issues of high complexity. Our *eHealth-delivered health coaching intervention* can potentially surmount the problem of delivering obesity interventions in busy practices, while supporting remote activity monitoring. mHealth is a promising adjunct to conventional therapies that improve adherence using automated health behavior change³²⁻³⁹. It can overcome the limits of counseling which heavily rely on self-motivation⁴⁰. Yet, devices alone insufficiently achieve sustained engagement in health behavior change in the absence of facilitation and support by coaches⁴¹. Emerging telehealth systems^{42,43} can fill a coverage gap^{44,45} by providing rural patients opportunities to access high quality specialty obesity care⁴⁶⁻⁴⁹. This modality can address the access and distance barriers faced by rural adults⁵⁰. *The project conceivably may alter care delivery by offering innovative and practical strategies to improve patient, system and practice-based outcomes*. Our strategy aligns with the NIH Strategic Obesity Plan, the Institute of Medicine's call for Telehealth Research⁵¹, and Medicare's population-health vision for improving access and delivering high-value care to an at-risk population⁵² with obesity in rural areas^{46,53}. The results will inform a future effectiveness study designed to improve outcomes and health of an emerging demographic with obesity⁵⁴, all which may reduce health costs⁵⁵. Our approach may satisfy a significant service mismatch of improved health care quality^{44,45} while redefining novel delivery processes for achieving efficiencies in an overburdened system.

INNOVATION

The proposed *eHealth-delivered health coaching obesity intervention* is innovative because it proposes to:

- Conduct the first pragmatic pilot using rural obese adults assessing health coach delivered IBT augmented by a remote monitoring device in a home-based program, with potential for scalability to other systems;
- Move beyond conventional methods of research-based obesity interventions using in-person clinician visits that integrates telehealth and mHealth into health coach based care to facilitate behavioral weight loss;
- Advance health promotion science using home-based Telehealth in rural areas allowing its incorporation into a real-world setting to support long-term adherence to lifestyle change;
- Use a unique mHealth approach with open-source application coding and a future basis for ecological momentary assessment extending beyond commercial devices that are at risk for becoming obsolete;
- Incorporates emerging technology into a comprehensive care model in obesity care;
- Create collaborations with mHealth technologists and telehealth experts allowing for translation of innovative laboratory-based technologies into practical applications for medically complex populations in rural settings;
- Use mixed-methods to identify factors leading to behavioral change using technology in the study population;
- Apply lessons learned from this study to other disadvantaged, low-income disparity populations.

APPROACH

Study Design: A single-arm, mixed-methods study that will adopt a pragmatic delivery approach to: a) assess the intervention's feasibility/acceptability; b) investigate the potential effectiveness; and c) ascertain outcomes of implementation. We will recruit 30 obese patients from the D-H Weight & Wellness Center (DH-WWC) to participate in a 12-week pilot that includes monthly assessments and qualitative semi-structured interviews.

Study Site: D-H, in Lebanon, NH, serves 1.5 million persons in New Hampshire and Vermont. Demographics mirror a typical rural New England town (95.4% Caucasian⁵⁶). The DH-WWC is a specialty referral-based obesity clinic whose aim is to improve the health and wellness of patients with obesity. The clinic uses the Epic electronic health record (EHR), and has rooms for interviews, assessments, and video-conferencing.

Selection Criteria: For the purposes of this pilot, we limited inclusion criteria to: community-dwelling, English-speaking patients (age 18-65 years; BMI $\geq 30\text{kg}/\text{m}^2$) with home Wi-Fi high-speed Internet and clearance from their clinician. Patients with dementia (lacking consent), bariatric surgery, severe mental or life-threatening illness, substance use, or exercise contraindications⁵⁷ are excluded as these criteria interfere with the possible efficacy of the intervention. Future pragmatic trials will relax the criteria to allow a pragmatic interpretation.

Study Population/Recruitment: The DH-WWC evaluated 315 new patients in 2016 (current waitlist ~ 3 mo.). As research director, the PI has access to subjects. To meet a target of n=30, $\sim 10\%$ of subjects would need to be enrolled. Staff will receive an overview at a weekly meeting. A research assistant (RA) will screen booked subjects by EHR review and identify eligible subjects. At the visit, the RA will proceed with a 2-way discussion focusing on the study goals, answering queries, providing contact details, and obtaining consent and baseline measurements. A Callahan score⁵⁸ ≥ 4 and no EHR diagnosis of dementia will assure competence for consent.

Retention: To minimize dropouts, we will provide feedback (ie: weight), frequent contacts, study incentives for assessments, and assertive outreach with the primary care provider (to engage partnerships). We anticipate that the duration of the pilot and patient motivation will lead to favorable retention.

Baseline Measures: We will review EHR records for: age, race, co-morbidity, education, medications, and habits. We will ask about social support^{59,60} at baseline.

Intervention Description: The pilot comprises of five components listed below which provide access to specialty obesity care to rural obese adults, and enhance it with technology (telehealth and remote monitoring):

a) **Team-based care:** As in other US-based specialty obesity centers, the DH-WWC is an interdisciplinary, team-based, specialty clinic overseeing each patient's care: a physician or associate provider formulates a medical plan and counsels on obesity's adverse effects; a nurse assists in triaging medical concerns and manages drug therapy; a psychologist evaluates the patient for barriers to weight-loss such as untreated or underdiagnosed mental health disorders; and a dietitian counsels the patient on nutrition/energy needs for achieving weight loss through nutritional therapy. The health coach is supervised by the clinician.

b) **Health coaching:** In the DH-WWC Healthy Lifestyle Program, a health-coach led program plays an integral role in assisting with patient tracking, data gathering, self-monitoring, facilitating educational sessions and connecting patients and families with local resources. Coaches are trained in avoiding weight bias and, undergo specific motivational interviewing training, use shared decision-making, and reframe obesity as a chronic disease. They complete select wellness coaching programs, pass certification exams and serve as the program anchor, facilitating care coordination, executing treatment plans and setting SMART goals (specific, measurable, agreed upon, realistic, time-based). Content is based on national guidelines⁶.

c) **Telehealth:** Weekly coaching sessions will be conducted by video-conferencing in lieu of in-person visits. [name] telehealth team will configure an Android tablet (using the HIPAA compliant software, Vidyo⁶¹) to the subject's home intranet remotely, and will provide training to both patients and staff. The interface has easy access using simple taps. The coach's computer will have similar software. Added coaching support is offered ad-hoc, as in usual care, using on-demand connectivity. Subjects will be located in their homes.

d) **Messaging:** Currently, coaches send messages via the Epic integrated EHR patient portal, used in >40% of US medical centers. 'Push' message notifications to the tablet's face screen are received indicating a message is waiting for review. Within 48 hours, coaches are notified if messages are read, and if not, the coach can contact the patient by phone. Communication is confidential, documented, and tracked.

e) **Remote Monitoring:** The *Amulet* is an mHealth wrist-worn device with remote sensing and self-monitoring capabilities, functioning independently of a smartphone (battery life lasts >9 days). A 9-axis gyroscope, accelerometer, magnetometer and sensor captures motion, activity type, exercise, and speed data. As part of [name] K23, *Amulet* applications were developed to measure steps, strength, and activity (sedentary, walking, running). Two-way data transfer occurs via a micro-SD card, or low-energy Bluetooth 4.0 to a secure cloud-based repository that is accessible to the team. Predetermined one-line automated scripts (if goals are not met), prompts, and asynchronous messaging can be sent by staff. Programmable reminders (blinking lights, text, haptic buzzer) and audio-visual feedback allow the *Amulet* to celebrate goal attainment.

Outcomes Measures: These were chosen based on their validity, brevity and presence within the HER:

Table 1: Study Variables and Objective Outcome Measures

Aim 1: Feasibility and acceptability of an eHealth-delivered health coaching obesity intervention						Timepoint			
Domain	Outcome/Co-Variate	Instrument	Adm	Length	Source	0	1	2	3
Feasibility	Recruitment/Retention	Eligibility, enrollment, dropout data	RA	---	Study Log	✓	✓	✓	✓
	Engagement/Assessments	>80% attend + complete sessions	RA	---	Study Log	✓	✓	✓	✓
Acceptability	Satisfaction of Intervention	Semi-structured interview	RA	30 min	Participant			✓	
	Patient Satisfaction	Yip Telemedicine questionnaire ⁶²	Self	15 item	Participant			✓	
Aim 2: Potential effectiveness in improving weight, physical function and self-reported health						Timepoint			
Domain	Outcome/Co-Variate	Instrument	Adm	Length	Source	0	1	2	3
Participant Level Outcomes	Anthropometry	Weight/body mass index	CS	---	Participant	✓	✓	✓	✓
	Physical function	6 minute walk test (6MWT) ⁶³	CS	6 min	Participant	✓			✓
	Diet/Exercise Measures	REAP-S ⁶⁴ /IPAQ ⁶⁵	Self	16/7 items	Participant	✓			✓
	Subjective Health	PROMIS general health 10 ⁶⁶	Self	10 items	Participant	✓			✓
	Readiness to Change	URICA ⁶⁷	Self	12 item	Participant	✓	✓	✓	✓
Aim 3a: Ascertain the extent to which the intervention works on implementation outcomes						Timepoint			
Domain	Outcome/Co-Variate	Instrument	Adm	Length	Source	0	1	2	3
Adoption	Workflow adoption	Qualitative Interviews	RA	30 min	Staff				✓
	Staff adoption	Evidence-based practice adoption ⁶⁸	RA	12 item	Staff				✓
Implementation	Organizational Change	General Organizational Inventory ⁶⁹	RA	12 item	Staff				✓
Compatibility	Patient Perception of Value	Willingness to Pay ⁷⁰	Self	2 item	Participant	✓			✓

ADM- Administration; CS – clinical staff; IPAQ – International Physical Activity Questionnaire; PROMIS: Patient Reported Outcome Measures Information Systems; RA: research assistant; REAP-S: Rapid Eating Assessment for Participants – Shortened Version; 6MWT: 6-minute walk test; URICA: University of Rhode Island Change Assessment: Short Form for Physical Health Behavior State.

Aim 1: Evaluate the feasibility and acceptability of an eHealth-delivered (remote monitoring and video-conferencing) health coaching obesity intervention in a rural, academic, specialty obesity clinic.

Feasibility: The following rates will be computed: screened for inclusion ($\# \text{ screened} \div \# \text{ potentially eligible}$); eligibility [$\# \text{ screen positive} \div \# \text{ screened for inclusion}$]; enrollment [$\# \text{ enrolled} \div (\# \text{ screen positive} \& \text{ eligible})$]; completion ($\# \text{ completing sessions} \div \# \text{ enrolled}$); assessment ($\# \text{ completing all assessments} \div \# \text{ enrolled}$). We will assess entry criteria (reasons for dropout/non-adherence) and time to collect data. Enrollment success will be defined as 30 patients. Adequate retention is defined as a dropout rate of <20%. Completion of >80% of post-study measures will be defined as adequate. Attending >80% of sessions will be considered acceptable. Staff will track equipment, software or technical issues (malfunctions, data loss, hardware) in a journal.

Acceptability: Qualitative interviews will ensure the appropriateness of the pilot and its strengths/weaknesses. The RA will conduct, record, and transcribe each 30min interview. Field notes, questions, and themes outlining the content/context allows for codebook development, tailoring it to the subject's needs in the future. Topics include: feasibility, acceptability; missing features; telehealth's impact (including sound/video quality); Amulet's usability and perceived barriers to use; complexity and flaws; strategies for improving compliance; feedback. Quantitative data will be measured using the 15-item, 5-point scale (*Telemedicine satisfaction questionnaire*⁶²).

Data Analysis: The analysis of Aim 1 is primarily descriptive. Data will be analyzed as follows:

- Qualitative Data: Thematic analysis⁷¹⁻⁷³ will be conducted by two researchers who will independently read transcripts, and conduct open coding⁷⁴. This enhances research rigor by allowing for different viewpoints⁷⁵. Through data immersion, focused coding using themes identified during open coding permits defined analyses⁷⁴. Codes will be derived *a priori* from interviews, and inductively derived from qualitative data, after which, the query tool will retrieve text by code, reviewed for content, relevance, and prevalence of themes.
- Statistical Analyses: Descriptive statistics (means, medians, proportions, 95% confidence intervals [CI]) will be computed for feasibility/acceptability. Telemedicine satisfaction will be assessed only at 12 week follow-up
- Sample Size Considerations: For the pilot, we estimation the proportion of patients attending and completing 10 of 12 scheduled sessions. If this proportion is 80%, then the half width of the expected 95%CI based on 30 enrolled patients is 14.3%, based on a normal approximation for binomial data.

Aim 2: Assess the potential effectiveness of an eHealth-delivered health coaching obesity intervention in improving weight, physical function and self-reported health in adults with obesity.

Objective & Subjective Participant-Level Outcomes:

- Weight & BMI: Weight will be measured using a Seca 770 analyzer (in clinic) and by the Omron HBF-514 (at home remotely). Target weight loss is defined by >5% of weight. BMI is calculated by Quetelet's formula⁷⁶.
- Physical function: *6-Minute Walk (6MWT)*⁶³ is a cardiovascular fitness surrogate measuring distance (normal 400-700m)^{77,78} related to function. A clinically important difference is 50-55m⁷⁹.
- Diet/Exercise: The Rapid Eating Assessment for Participants (REAPS)⁶⁴ is a 16 item survey (score 13-39) of diet habits. The 7-item international physical activity questionnaire (IPAQ) measures health-related activity⁶⁵.
- Subjective Health: The 10-question, non-proprietary *Patient Reported Outcomes Measurement Information Systems General Health-10 (PROMIS)*⁶⁶ captures physical, mental and social aspects of quality of life.
- Readiness to Change: The University of Rhode Island Change Assessment⁶⁷ is a 12 item questionnaire assessing one's stages of change based on contemplation, action, maintenance and pre-contemplation.

Data Analysis: Aim 2 will evaluate potential effectiveness of the intervention on patient outcomes:

- Statistical Analyses: We will assess % weight loss and BMI change (primary outcomes), and change in the 6MWT, REAP-S, IPAQ, PROMIS and URICA (secondary outcomes). Linear/non-linear mixed effects models will evaluate weight, BMI and URICA change over time. To account for repeated measures and variation in trajectory over time, models will include random individual-level intercepts and time trends. A significant coefficient for the mean trend over time will indicate changes in outcomes. All data will be included as the models are robust to data missing at random under the assumptions of a linear mixed model. Paired t-tests will assess the change between baseline and follow-up in 6MWT, REAP-S, IPAQ and PROMIS.
- Sample Size Considerations: This pilot study intends to help develop future studies to evaluate recruitment, feasibility, acceptability and outcomes. Given the longitudinal nature of the data, a key parameter driving the future design is the intraclass correlation coefficient (ICC), a measure of dependence between observations taken on the same person. With 30 participants and a mean of 10 observations/person, we should be able to distinguish between a fairly low ICC of 0.15 versus an alternative of 0.34, based on a one-sample hypothesis test with a significance level of 0.05 and a power of 90%⁸⁰. For the primary outcome of % weight loss, using

a SD of 10.1%, the 95% CI would have half width of 3.6% based on our sample of 30, assuming a normal distribution.

Aim 3: Ascertain the extent to which the intervention works within an existing specialty obesity clinic on implementation outcomes such as workflow adoption, organizational change and compatibility.

Objective and Subjective Adoption, Implementation and Compatibility-Level Outcomes:

- Adoption Domain: *Workflow Adoption*: Questions using semi-structured interviews (methods per Aim 1) from the staff's experience with the intervention (whether it enhances/interferes with workflow; sustainability; technical or other difficulties in delivering care) will be explored. *Staff Adoption*: Haug's 12-item *Measure of Evidence-Based Practice Adoption*⁶⁸ assesses stage of change, experience, attitudes, organization barriers and strategies to support evidence-based practices (1-5 point scale - strongly disagree to agree).
- Implementation Level: *Organizational Change*: General Organizational Index (GOI)⁶⁹ is an interview of 11 domains with a 5-point rating of: program philosophy, commitment, client eligibility and identification, health promotion plan and its treatment, training, process and outcome monitoring, assessment, quality assurance, choice supervision, & penetration. It has reliable inter-rater agreement and internal consistency.
- Compatibility: *Patient Perception of Value*: Two questions will assess *Willingness to Pay (WTP)*⁷⁰ – whether they would pay for telemedicine delivery of the intervention in lieu of in-person travel time or cost.

Data Analysis: We will use mixed-methods to analyze data from Aim 3 as follows:

- Qualitative Data: Interview data will be managed and analyzed using *Dedoose* as described in Aim 1.
- Statistical Analyses: Descriptive statistics (means, medians, 95% CI) for adoption, organizational change will be assessed at follow-up only. Changes in WTP will be estimated using a paired 2-sample t-test.
- Sample Size Considerations: For changes from baseline on WTP, there will be 80% power to detect large differences in change from 0.32 to 0.28 times a SD assuming a range of within-person correlations (0.2-0.4).

Data Management: Our team is experienced in pilot delivery, data management/acquisition, and validation procedures including: a) health coach training; b) continuous feedback; and c) final data editing. The PI and co-l's will meet staff regularly, supervise and identify quality control issues early to address them promptly. Non-HER entered measures will be collected by the RA using REDCap⁸¹, a secure web/tablet based data collection tool. The Analytics Institute manages a DH-WWC patient registry who will facilitate data extraction. Interviews will be recorded in duplicate using a digital tape recorder. Records will be kept in a locked cabinet. Identifiers will be assigned at enrollment and kept behind the D-H firewall, with a password protected linked file. Data will be exported to *Dedoose* and *R* for analysis with complete labeling intact (variables, labels, missing values)

Potential Problems/Alternative Strategies: We anticipate that: a) adults may lack technology skills – our team can provide ongoing user support to participants; b) attrition will occur – yet, due to the recruitment of motivated persons and ongoing support^{82,83} this will be low; c) minorities will be under-represented consistent with rural New England's demographics - our region's socioeconomic diversity can create a strategy that can be adopted in other regions to enrich the sample with minorities; d) our criteria maximize external validity and limit internal validity used in randomized trials – consistent with pragmatic trials⁸⁴; e) technology advances quickly raising the potential of obsolescence - *Amulet* was purposefully designed for capabilities of advanced capacity; and f)adverse outcomes exist - exercise contraindications and medical clearance are considered with symptoms prompting further evaluation. We do not anticipate an increase in risk with video-conferencing and eHealth. All other elements are components of standard care and hence would not alter the treatment plan.

Study Timeline/Benchmarks to Success: The schedule for the anticipated funding is presented below:

MONTH	1	2	3	4	5	6	7	8	9	10	11	12
Staff Training/Preparation of Site	X											
Recruitment & Enrollment		X	X	X	X	X	X	X	X			
Intervention/Data Management/Analysis			X	X	X	X	X	X	X	X	X	X
Manual Development/R01/Manuscript											X	X

PROPOSED R01 PROJECT GRANT

This knowledge will generate promising data to support the design and submission of an adequately powered randomized trial to the National Institute of Diabetes, Digestive and Kidney (PA16-17-021) evaluating the effectiveness of the *eHealth-delivered health coaching obesity intervention*. The results will permit sample size calculations to detect a range of effect sizes for an eHealth arm (intervention) vs. usual clinic-based care. These methods will allow diverse recruitment across the regional D-H system, and be applied to other sites (ie: primary care) and populations. If effective, we can adapt the pilot to focus on sustainability of weight loss.

LITERATURE CITED

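### H1a calls an intervention with remote monitoring feasible, but every Aim 1 feasibility rate counts recruitment, video sessions or assessments, and none counts Amulet use or data yield

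*Combined protocol and SAP*

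**What the plan says.** The hypothesis (Specific Aims, H1) opens with "An eHealth-delivered health coaching obesity intervention using video-conferencing and remote monitoring is", and its feasibility limb, H1a, then gives two thresholds: "feasible (>80% of subjects will enroll; >80% of enrollees will complete the intervention". H1b is acceptability, judged by interviews and the Yip questionnaire, with no numerical threshold.

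Aim 1, Feasibility, lists five rates: screening, eligibility, enrolment, completion and assessment. The completion numerator is patients completing sessions, and the assessment numerator is patients completing all assessments. Both are divided by the number enrolled. The further benchmarks are "Enrollment success will be defined as 30 patients", dropout below 20%, more than 80% of post-study measures completed, and more than 80% of sessions attended. Table 1 has two feasibility rows, one for recruitment and retention and one for engagement and assessments. Engagement is defined there by sessions.

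The Intervention Description lists five components. Item (c) makes the weekly coaching sessions video calls. Item (e), remote monitoring, is the Amulet, whose data move by micro-SD card or by "low-energy Bluetooth 4.0 to a secure cloud-based repository that is accessible to the team".

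The device also enters the evaluation in descriptive form. Under Aim 1, Feasibility: "Staff will track equipment, software or technical issues (malfunctions, data loss, hardware) in a journal". The same paragraph provides for reasons for dropout and non-adherence. The patient interviews cover Amulet usability and barriers to use, and the Aim 3 staff interviews cover technical and other difficulties in delivering care.

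**The concern.** The hypothesis names two technologies, and the numerical criteria measure one of them. A patient who attends all 12 video calls and never wears the Amulet counts as a full completer.

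One might hope that completing the intervention, in H1a's words, includes the monitoring. The Aim 1 text closes off that reading. Completion is defined by sessions, and the sample-size paragraph sizes it on 10 of 12 sessions. No other aim fills the gap: no outcome in Table 1 is derived from the Amulet, and physical activity under Aim 2 comes from a self-completed questionnaire.

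At stake is what the pilot can tell the next study. The section on the proposed R01 says the results will support a randomized trial of an eHealth arm against usual clinic-based care. The planners of that trial would want to know how often device data actually arrived. As written, the plan yields no such figure, yet H1a could be reported as met for the whole intervention.

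**Working it through.** **1. The plan's own precision figure.** Inputs from Aim 1, Sample Size Considerations: p = 0.80, n = 30, normal approximation, 95% level.

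Half-width = 1.96 × √(0.80 × 0.20 / 30) = 1.96 × 0.0730 = 0.143, or 14.3%. This reproduces the stated value. It concerns session attendance only.

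**2. What each Aim 1 criterion counts.**

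| Criterion | What is counted | Uses Amulet data? |
|---|---|---|
| Screening and eligibility rates | recruitment flow | no |
| Enrolment rate; 30 enrolled | recruitment flow | no |
| Completion rate; attendance >80% | video sessions | no |
| Assessment rate; post-study measures >80% | assessments | no |
| Dropout <20% | patients leaving the study | no |

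**3. The completion limb of H1a.** More than 80% of 30 means more than 24, so at least 25 of 30 (83%). At patient level, 80% of 12 sessions is 9.6, so more than 80% means at least 10, which agrees with the 10 of 12 in the sample-size paragraph.

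The probability of meeting the limb is P(X ≥ 25), with X binomial (30, p) and p the true share of enrollees who complete their sessions. The documents give no expected p beyond the 80% used for precision, so the values below are assumed.

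| Assumed p | P(X ≥ 25) |
|---|---|
| 0.80 | 0.428 |
| 0.85 | 0.711 |
| 0.90 | 0.927 |
| 0.95 | 0.997 |

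The formula has no term for wear or data yield. For a given p, the probability is the same at 0% device use as at 100%.

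**4. Could a device rate be estimated usefully with n = 30?** The Wilson 95% interval for 24/30, with z² = 3.8416, is:

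- Centre = (0.80 + 3.8416/60) / (1 + 3.8416/30) = 0.8640 / 1.1281 = 0.766.
- Half-width = 1.96 × √(0.16/30 + 3.8416/3600) / 1.1281 = 0.1568 / 1.1281 = 0.139.
- Interval: 62.7% to 90.5% (unrounded upper limit 90.49%), that is 63% to 90% in whole per cent.

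The documents give no figure for wear or yield, so a range is shown. With the plan's own formula, the half-width at n = 30 is 17.9% for a true rate of 50%, 16.4% for 70%, 14.3% for 80% and 10.7% for 90%. At equal proportions, the precision is exactly that of the planned session rate.

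**The case against.** The strongest reply is that the plan does look at the device. The journal expressly includes data loss, reasons for non-adherence are collected without restriction to sessions, and patients and staff are interviewed on usability and technical difficulties. Universal non-use would very probably come to light. The Aim 1 analysis is described as mainly descriptive, and nothing in the documents makes the next trial, or the Amulet's place in it, conditional on H1a. A binding device criterion in a 30-patient single-arm pilot is then a matter of preference.

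Much of this stands, and it rules out several stronger readings that a reader might infer:

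- That device feasibility is never examined. It is examined, but without a rate.
- That H1 as a whole can pass with the device unused. H1b draws on interviews that cover the Amulet, so the gap is sharpest for H1a.
- That 25 of 30 completers satisfy H1a. They satisfy its completion limb only; the enrolment limb must also be met.
- That half of the intervention goes unmeasured. The Amulet is one of two technologies named in H1, but one of five listed components.
- That an untested component will necessarily go into the next trial. The documents do not say so.

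The reply does not remove the mismatch. A working device left in a drawer is not a malfunction. Reasons for non-adherence do not say how common it was, and interview themes have no denominator. A numerical rule that never refers to the device cannot support a numerical conclusion about it.

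**Conclusion.** The point holds for H1a. Followed exactly as written, its two thresholds and all the Aim 1 rates can be met whatever the Amulet use or data yield, although the hypothesis names remote monitoring. The fault is one of definition; the plan's arithmetic is correct.

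The size of any actual shortfall is unknown. No document gives a wear or yield figure, and zero use is only the limiting case that shows the rule does not respond to the device. The pass probabilities rest on assumed session-completion rates and on independent patients. The 24/30 interval shows only that such a rate can be estimated about as well as the planned one. It says nothing about likely device use, and 24/30 would not itself exceed 80%.

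The change is worth making before the results are interpreted. It invalidates none of the planned analyses.

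**What to change.** Add one rate to the Aim 1 feasibility list: the number of enrollees with Amulet data received, by Bluetooth or micro-SD card, on at least a pre-specified share of intervention days, divided by the number enrolled, with a 95% CI. Report the mean percentage of intervention days with data beside it.

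State that data received is a proxy for wear. An unworn device may transmit, and a worn one may fail to transfer. Use the technical journal to separate transfer failure from non-use where possible.

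Base any statement that remote monitoring is feasible on this rate. If the team does not want the extra rate, limit the H1a conclusion to video-conference coaching. Whether the rate also becomes a pass/fail criterion, and which share of days is used, are choices for the team. The documents set no wear standard, so the share should be fixed before the data are seen.

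The cost is modest but more than one sentence. A short definition of a valid day must be written, because the documents give no wear schedule or transfer interval. A data extract must also be specified, since Data Management does not mention Amulet data. Patients would have no additional assessments. The main downside is that the result could be unfavourable.
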